CRF will be determined using the Functional Assessment of Chronic Illness Therapy (FACIT-Fatigue) survey instrument. The FACIT is a 13-item subscale developed to identify a finite set of concerns specific to fatigue. The responses to the 13 items on the FACIT-Fatigue questionnaire are each measured on a 4-point likert scale, with score ranging from 0 to 52. The FACIT-Fatigue scale has been validated in patients with cancer and showed excellent internal consistency and reliability. The following biomarkers of inflammation will be assessed at the Hackensack UMC: (1) High sensitivity CRP (hsCRP) - Serum hsCRP will be measured on the Vitros 5,1 FS Chemistry platform via an immunoassay with a reportable range of 0.10 -15.00 mg/L, and intra- and inter-assay CVs of 1.8-4.0%. (2) Serum fibrinogen and (3) Ferritin will be measured using standardized clinical protocols. All assays have intra- and inter-assays coefficient of variations <10%. We will collect CBC data at each blood draw for correlative and explorative purposes.

Secondary Outcomes

Cancer-related healthcare quality of life (HRQOL) among participants in the study will be measured using the Functional Assessment of Cancer Therapy (FACT) system questionnaires. The HRQOL measures four different domains (physical well-being, functional well-being, emotional well-being, and social/family well-being). FACT-B is a breast cancer specific module that will be used to reflect patients' concerns; moreover, they are reliable, reproducible, and have been validated in numerous studies. Higher scores on the FACT questionnaires reflect higher QOL. Post hoc analysis will be performed to associate RT treatment parameters against differences in outcomes, including utilizing the following pre-specified parameters: heart V5, lung V20, utilization of suprACLAVICULAR field (yes/no), utilization of suprACLAVICULAR field with axillary coverage (yes/no). These will potentially be hypothesis-generating and no Bonferroni corrections will be applied.

Sample size Considerations

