In this study participants are randomized into two groups: a structured exercise intervention group and a usual care control group. It is expected that there will be two levels of fatigue measurements: at baseline and after the exercise intervention. Our sample size calculation is based on analysis of covariance (ANCOVA) comparing mean fatigue score differences between the two intervention arms at the end of intervention, adjusting for baseline. In our exercise intervention study ([name] et al, unpublished data, mean fatigue scores of 42.53 (SD=9.35) and 37.12 (SD=9.42) were reported for the intervention and control arms, respectively. In the same study, the correlation coefficient between baseline and after intervention fatigue scores was calculated as 0.64. With the above guidelines and a level of significance of $\alpha=0.05$ (two-sided), we will use randomize 40 women/arm to obtain statistical significance between the arms with 90% power for the overall ANCOVA F-ratio.

Statistical analysis

Baseline characteristics will be compared between the two intervention groups using two-sample t-test or Wilcoxon rank-sum test depending on whether the t-test assumptions are satisfied or not. Suitably transformed variables will be used when necessary. Categorical variables will be compared between the two groups using chi-square tests or Fisher's exact test. The major analytical tool for addressing the specific aims of this study is linear mixed modeling for repeated measures. Study endpoints will be measured three times in each participant in the study, and it is expected that measures on the same individual will be correlated. We will also examine whether the variance of repeated measures changes over time. An appropriate correlation structure will be selected depending on whether there is a trend of variance with time or not. For each outcome measure of interest, a linear mixed repeated measures model will be fit to evaluate the main effects of time, study group, and group-by-time interaction. Known confounders and other covariates will be included in the linear mixed models if their individual bivariate associations with both the group variable and outcome are significant at 10% level.

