We hypothesize that participants in the intervention group will have lower average fatigue scores compared to the usual care group after the intervention. For Aim 1 and Aim 3, "change scores" will be defined as the difference between baseline score and 4 week, (end of radiation treatment) score. Change scores will be compared between the two groups using t-test or Wilcoxon rank-sum test. An ANCOVA model will be utilized to assess group differences in change scores adjusting for covariates including age. We hypothesize that participants in the structured exercise intervention group will have lower levels of fatigue (Aim 1) and lower levels of inflammatory biomarkers (Aim 3) compared to baseline at follow-up visits as compared to the usual care control group. We hypothesize that there will be at least partial normalization of both the fatigue levels reported and the inflammatory biomarkers to baseline by the 4-week follow-up visit. Linear mixed models as described above will be used to compare fatigue scores and inflammatory biomarkers levels over time across the study groups. For Aim 2, we will report rates of acceptability and adherence at baseline and end of intervention. We will use the binomial test to compare acceptance and adherence rates between the two intervention arms. Baseline and end of intervention acceptability levels evaluated using the Wilcoxon sign-rank test or McNemar's test (or generalized McNemar's test) for numerical and categorized outcomes, respectively.

A Graduate Research Assistant (GRA) will assist with data collection for the survey data. The GRA will collect log data of the women exercising using the Pedlar device. There is an hourly reimbursement for GRA labor without incentive. This has been approved via the Development Grant.

f. Significance

This study will contribute to the literature on the role of concurrent radiation treatment and moderate-intensity exercise in reducing cancer-related fatigue and improving HRQOL among breast cancer patients undergoing.

This study will also provide pilot data on the correlation of inflammatory markers with exercise-related changes in fatigue and other HRQOL measures in breast cancer patients undergoing RT. The strengths of this study include the use of an “in-office” easy to use exercise intervention that reduces participant burden, the timing of exercise inception that coincides with RT inception, and use of biomarkers.

g. Future Plans

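### The analysis scale for hsCRP under Aim 3 is not fixed, and a plain change score would lose power if the marker is right-skewed

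*Combined protocol and SAP*

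**What the plan says.** All of this is in section e, Methods.

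- **Assay.** Under Outcomes, Primary outcomes, hsCRP is listed among the inflammation biomarkers and measured by an "immunoassay with a reportable range of 0.10 -15.00 mg/L", with "intra- and inter-assay CVs of 1.8-4.0" per cent. The text does not say what is recorded for a result outside that range.
- **Change score.** Under Statistical analysis, the Aim 1 and Aim 3 change score "will be defined as the difference between baseline score and 4 week" value. No log or ratio scale is named.
- **Tests.** "Change scores will be compared between the two groups using t-test or Wilcoxon rank-sum test". Then: "An ANCOVA model will be utilized to assess group differences in change scores adjusting for covariates including age". Age is the only covariate named, and the baseline marker value is not.
- **Longitudinal model.** "Linear mixed models as described above will be used to compare fatigue scores and inflammatory biomarkers levels over time across the study groups". No scale is given there either.
- **Transformation.** "Suitably transformed variables will be used when necessary". This sentence stands between two sentences on comparing baseline characteristics and names no variable, scale or trigger.

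**The concern.** The fatigue score is bounded, so a plain difference is a natural outcome for it. The plan applies the same definition to hsCRP, a concentration whose reportable range runs from 0.10 to 15.00 mg/L (15.00 / 0.10 = 150). If such a marker is right-skewed, the variance of raw change is driven by the few women with the highest values, and a proportional effect of exercise is hard to see among 40 women per arm.

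The plan also leaves open whether the t-test or the Wilcoxon test is used on change and whether anything is transformed, so the scale could be chosen after the data are seen. The biomarkers sit under the primary outcomes heading and are the whole of Aim 3. The abstract asks whether inflammation mediates the effect on fatigue, and Future Plans intends to build biomarker endpoints for a larger trial on these data.

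**Working it through.** **1. The plan's own figure.** The only sample-size calculation is for fatigue. Difference: 42.53 − 37.12 = 5.41. Pooled SD: √((9.35² + 9.42²)/2) = 9.385. Residual SD after baseline adjustment: 9.385 × √(1 − 0.64²) = 7.211. At two-sided 0.05 and 90% power, the normal approximation gives 38 per arm and the noncentral t gives 39. Power at 40 per arm is 91.2% (noncentral t). The stated 40 reproduces. It does not bear on hsCRP, for which the plan states no power.

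**2. Assumptions for hsCRP (none is in the documents).** Lognormal values; baseline median M and log SD s as tabulated; baseline to 4-week correlation ρ = 0.7 on the log scale; controls rise by a factor of 1.3; exercise multiplies the 4-week value by 0.6; 40 per arm; two-sided 0.05.

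**3. Log-scale power in closed form.** The effect is |ln 0.6| = 0.511.

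- Log change: SD = s√(2(1 − ρ)). For s = 1.0 this is 0.775, the standard error is 0.775 × √(2/40) = 0.173, the noncentrality is 0.511/0.173 = 2.95, and power is 83%. For s = 1.1 it is 75%, and for s = 1.2 it is 68%.
- Adjusted for baseline log hsCRP: SD = s√(1 − ρ²). For s = 1.0 this is 0.714, the noncentrality is 3.20, and power is about 88%.

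**4. Raw-scale power by simulation** (20,000 trials per row, no assay limit applied):

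| M (mg/L), s | Raw change, t | Raw change, Wilcoxon | Log change, t | Log, baseline-adjusted |
|---|---|---|---|---|
| 1.5, 1.0 | 53% | 73% | 83% | 88% |
| 2.5, 1.0 | 53% | 73% | 83% | 88% |
| 2.5, 1.2 | 33% | 56% | 68% | 74% |
| 4, 1.1 | 42% | 65% | 75% | 81% |

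The log-change test gains about 29 to 35 points over the raw t-test and about 10 to 12 over Wilcoxon. Shorter runs moved entries by one to three points.

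**5. What the 15.00 mg/L limit does, if values are set to it.** The true raw difference in mean change is M × 1.3 × (0.6 − 1) × exp(s²/2); for the first row, 1.5 × 1.3 × (−0.4) × 1.649 = −1.29.

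| M, s | Women above 15 at either visit | Raw difference: true, then set to 15 | Shrinkage | Raw t power: no limit, then set to 15 | Log-change ratio after clipping (true 0.60) |
|---|---|---|---|---|---|
| 1.5, 1.0 | 2% | −1.29, −1.15 | 11% | 53%, 60% | 0.61 |
| 2.5, 1.0 | 6% | −2.14, −1.65 | 23% | 53%, 66% | 0.61 |
| 2.5, 1.2 | 11% | −2.67, −1.61 | 40% | 33%, 50% | 0.62 |
| 4, 1.1 | 18% | −3.81, −2.01 | 47% | 42%, 62% | 0.64 |

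Clipping shrinks a real raw mean difference but raises the power of the raw t-test, because it removes the extreme values. With no exercise effect (ratio 1.0), clipping left the mean difference near zero and rejection at about 5%.

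**6. A second set of assumptions.** With median 2, 3 or 5 mg/L, log SD 0.9 to 1.3, correlation 0.64 (borrowed from fatigue), ratio 0.65, control rise 1.0 or 1.3, and values clipped to the range, power is 24% to 60% for raw t, 30% to 62% for Wilcoxon, 36% to 71% for log change and 43% to 78% for log with baseline adjustment. The ordering is the same.

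**The case against.** The plan is not tied to a t-test on raw differences. It calls linear mixed modelling its major tool and applies it to the biomarkers. It offers Wilcoxon for change scores, and it allows transformation where needed, which nothing expressly limits to baseline variables. The biomarker results are described as pilot data, and the distribution used above is assumed.

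Much of this stands. Against Wilcoxon the gain is about 10 to 12 points, not 30. But no rule selects Wilcoxon for change scores, and it gives no effect estimate on a stated scale. The mixed model does not settle the scale: with complete data and an unstructured covariance, its group-by-time contrast at 4 weeks is the difference in mean raw change. The transformation sentence leaves the choice open.

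A reader might go further and infer that the assay cuts off the highest results, so that the exercise effect on hsCRP is understated and poorly tested for that reason. The documents do not support this. A reportable range does not say what is recorded above it; a laboratory may dilute and repeat. Appendix F, to which Table 1 refers for the biomarkers, is not in the text available, so laboratory handling cannot be checked. Setting values to 15 raised raw t-test power in all four scenarios and created no difference between arms when exercise had no effect.

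**Conclusion.** The point holds for the analysis scale. The plan defines the Aim 3 change as a plain difference and fixes no scale for hsCRP. Under the first set of assumptions, power is about 33% to 54% with a raw-change t-test and 56% to 73% with Wilcoxon, against 68% to 83% with a log-change t-test. These figures depend on hsCRP being right-skewed and on an assumed 40% reduction with exercise; if the marker were close to symmetric, the gain would largely disappear.

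The assay limit is secondary. The missing rule for out-of-range results is a gap in detail, and any attenuation is conditional on such values being clipped or dropped and on a real effect. If they were set to 15, the raw mean difference would shrink by about 10% to 47% under these assumptions, whereas the clipped log-scale ratio stays at 0.61 to 0.64 against 0.60. The point is confined to hsCRP: the documents give no range or distribution for fibrinogen or ferritin. Fatigue and its sample size are untouched.

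**What to change.** In Statistical analysis, Aim 3:

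- Define the hsCRP outcome as log(4 weeks) minus log(baseline), compared between arms with adjustment for baseline log hsCRP. Using log(4 weeks) as the outcome with the same covariate gives the identical group effect and confines censoring to the outcome.
- Use log hsCRP in the mixed model.
- Report the between-arm geometric mean ratio with its confidence interval.

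As a secondary addition, in Primary outcomes or Statistical analysis, state that a result outside 0.10 to 15.00 mg/L is treated as censored at the limit, not as missing, unless the laboratory reports a diluted value.

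The cost is a few sentences, with no extra patients or visits. The downside is that the result is a ratio, not a difference in mg/L. Dilution should not be presented as free: the documents mention no stored samples, so it would have to be arranged with the laboratory at the time of assay. The scale should be fixed before any unblinded biomarker data are examined.

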All participants in the study undergo RT as scheduled by their physician. The exercise intervention does not interfere with dose or timeline of RT. No specific requirements are made herein regarding prone or supine positioning, utilization of standard fractionation or hypofractionation, use of cardiac blocking or for utilization or omission of boost phase of radiation. These treatment decisions are completely at the discretion of the treating radiation oncologist. Adherence to the exercise intervention is achieved by offering participants flexibility in scheduling daily exercise, either before or after radiation treatment. Adherence is recorded in daily participation logs. Logs document participant identification, date, and length of time utilizing the Pedlar device. Participant retention efforts include a \$20 gift card incentive at baseline and one follow-up visit.

Assessments

Three assessments: at baseline, at 4-weeks into radiation course and at 4-week follow-up visit, will be assessed (see Table 1 below).

Table 1: Baseline and Follow-up Assessments

Assessment	Screening	Baseline (T0)	4 weeks (T1)	Follow-up visit (T2)
Eligibility (Appendix A)	X			
Informed Consent (Appendix B)	X			
Demographics (Appendix C)	X			
Medical history (Appendix C)	X			
Medications (from MD Consultation Note)	X			
Cancer and Treatment Summary (Appendix D)	X			
Performance Status	X			
Physical activity readiness questionnaire (Appendix C)	X			
Physical activity recall questionnaire (Appendix E)	X			
Blood tests for hematology (Appendix F)		X		
Vital signs and anthropometrics (Appendix G)		X	X	X
FACIT-Fatigue (in Appendix C)		X	X	X
FACT-B HRQOL (in Appendix C)		X	X	X
Inflammation biomarkers (Appendix F)		X	X	X
Adverse events assessments			X	X
Radiation Treatment Summary (by Treating MD)				X

Outcomes

Primary outcomes

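### The correlation structure of the main mixed model is chosen from the variance trend alone, which cannot show whether visits are equally correlated; an unstructured covariance should be pre-specified instead

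*Combined protocol and SAP*

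**What the plan says.** All of this is in the combined protocol and SAP.

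- **Role of the model** (Statistical analysis): "The major analytical tool for addressing the specific aims of this study is linear mixed modeling for repeated measures". For each outcome, "a linear mixed repeated measures model will be fit to evaluate the main effects of time, study group, and group-by-time interaction".
- **Data** (Statistical analysis): each endpoint is taken at three visits, and the plan expects within-woman correlation. The Assessments section places the visits "at baseline, at 4-weeks into radiation course and at 4-week follow-up visit" (T0, T1, T2).
- **Choice of structure** (Statistical analysis): "We will also examine whether the variance of repeated measures changes over time", and then "An appropriate correlation structure will be selected depending on whether there is a trend of variance with time or not".
- **Only documented correlation** (Sample size Considerations): "the correlation coefficient between baseline and after intervention fatigue scores was calculated as 0.64". No T1-T2 or T0-T2 value is given, and none at all for the biomarkers or FACT-B.

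The plan names no candidate structures, default, check of the correlation pattern, or robust standard error. Later in Statistical analysis, baseline-to-4-week change is also compared by t-test or Wilcoxon test and by ANCOVA. For T2 the mixed model is the only between-arm analysis named.

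**The concern.** Variance over time and correlation between visits are separate features of a covariance matrix. With equal variances, the three correlations may be equal, may fade with the gap between visits, or may follow another pattern. A check of variance cannot tell these apart, so the stated criterion is uninformative about the thing it is meant to select.

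This matters because a constant-correlation model uses one within-woman error for every pair of visits. If the pairs differ, that single value is too large for some change contrasts and too small for others. The plan hypothesises lower fatigue and lower biomarkers relative to baseline at the follow-up visits, compared with control, which is a contrast of this type. Unequal correlation is plausible here: T0 to T2 is the longest gap, and T2 falls after treatment while T1 falls during it.

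**Working it through.** **1. The plan's own figure.** Inputs: "mean fatigue scores of 42.53 (SD=9.35) and 37.12 (SD=9.42) were reported for the intervention and control arms", and a baseline-to-post correlation of 0.64. The difference is 42.53 − 37.12 = 5.41. The pooled SD is √[(9.35² + 9.42²)/2] = 9.385. The ANCOVA residual variance is 9.385² × (1 − 0.64²) = 52.0. Then n per arm = 2 × (1.960 + 1.282)² × 52.0 / 5.41² = 37.3, so 38 against the stated 40. Power at 40 per arm is 91.2% (noncentral F) against the stated 90%. The sample size reproduces, and it does not involve the mixed-model covariance.

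**2. Standard errors if constant correlation is used.** Assume equal variances, complete data and 40 per arm. For the arm difference in change from T0 to visit k:

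- true SE = SD × √[2(1 − r₀ₖ)] × √(2/40)
- constant-correlation SE = SD × √[2(1 − r̄)] × √(2/40), where r̄ is the mean of the three correlations
- ratio = √[(1 − r̄)/(1 − r₀ₖ)], and two-sided type I error = P(|Z| > 1.96 × ratio)

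Example with T0-T1 0.64 (documented), T1-T2 0.64 (assumed) and T0-T2 0.64² = 0.41 (assumed first-order autoregressive pattern): r̄ = (0.64 + 0.64 + 0.41)/3 = 0.563.

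- T1: true SE 1.78, model SE 1.96, ratio √(0.437/0.36) = 1.10
- T2: true SE 2.28, model SE 1.96, ratio √(0.437/0.59) = 0.86

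**3. Range over the unknown T0-T2 correlation** (T0-T1 and T1-T2 held at 0.64):

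| T0-T2 | r̄ | T1 ratio | T1 type I | T2 ratio | T2 type I |
|---|---|---|---|---|---|
| 0.64 | 0.640 | 1.00 | 5.0% | 1.00 | 5.0% |
| 0.55 | 0.610 | 1.04 | 4.1% | 0.93 | 6.8% |
| 0.50 | 0.593 | 1.06 | 3.7% | 0.90 | 7.7% |
| 0.41 | 0.563 | 1.10 | 3.1% | 0.86 | 9.2% |
| 0.30 | 0.527 | 1.15 | 2.5% | 0.82 | 10.7% |

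**4. Other patterns** (T0-T1 / T1-T2 / T0-T2, all but the first value assumed, same formula):

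- 0.64/0.64/0.70: T1 5.7%, T2 3.7% (direction reversed)
- 0.64/0.55/0.64: 4.1% at both (both conservative)
- 0.64/0.72/0.60: T1 5.4%, T2 6.8% (both inflated)

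**5. Simulation for 0.64/0.64/0.41** (20,000 trials, 40 per arm, constant correlation imposed in every trial):

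- Constant correlation, no effect: T1 3.2%, T2 9.5%. A repeat run gave 3.1% and 8.8%, on either side of the analytic 9.2% at T2.
- Unstructured covariance, no effect: T1 4.9%, T2 5.3%.
- Mixed-model change contrast at T1 with a true 5.41-point effect: power about 81% with constant correlation, 85% with unstructured.
- Two-degree-of-freedom group-by-time test with constant correlation: 5.7%.
- Plain arm difference at T2, not relative to baseline: 5.2%, so essentially undistorted.

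**The case against.** The strongest reply is that the plan never says it will use constant correlation. It promises an appropriate structure, and autoregressive, Toeplitz or unstructured forms are all possible when variance is flat. That stands. A reader might infer from the figures above that this trial has a T2 error rate of 9.5%. The documents do not support that: the figure is what would follow if constant correlation were always imposed under one assumed pattern.

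A reader might also infer that T1 is always conservative and T2 always anti-conservative. That is not supported either. Only the 0.64 baseline-to-post correlation is documented, and step 4 shows that the directions can reverse or coincide. The plan expects partial return to baseline by T2. That is a statement about levels rather than correlations, but it is a reason not to take steady fading for granted.

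Three further points stand. The group-by-time test, which the plan does name, is barely affected. No separate T2 contrast is specified as a test, although a change from baseline at follow-up is hypothesised. And the 4-week change-score test and ANCOVA do not use this covariance, so the drop from 85% to 81% concerns only the mixed-model contrast at T1. Choosing the structure after inspecting outcome data is a weakness of pre-specification, but no harm from it has been quantified, and variance can be inspected pooled across arms.

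What the reply does not rescue is the rule itself. It names a criterion, and that criterion carries no information about correlation.

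**Conclusion.** The point holds in a limited form. Choosing the structure from the variance trend cannot identify the correlation pattern, and it allows constant correlation where that is false. Under the illustrative assumptions (equal variances, complete data, T1-T2 0.64, T0-T2 0.41 to 0.55), constant correlation would give about 3 to 4% type I error at T1 and 7 to 9.5% at T2 for single-visit change from baseline. With equal correlations the cost is nil, and with other patterns the signs differ.

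The practical exposure is mainly the T2 change-from-baseline comparison, for fatigue and for the biomarkers, because no other between-arm analysis is named there. This is a cheap improvement to the plan. It does not undermine the sample size or the 4-week analyses.

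**What to change.** In Statistical analysis, replace the variance-trend rule with a fixed specification:

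- An unstructured covariance for all three-visit mixed models (three variances and three covariances), with Kenward-Roger degrees of freedom.
- One named fallback for non-convergence that does not rely on equal spacing of visits, for example a simpler structure with robust standard errors. Spacing may vary between women, because fractionation and boost are left to the treating radiation oncologist.

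This handles flat or trending variance and equal or unequal correlation, and it removes the data-driven step. The cost is about one sentence of text and a few extra nuisance parameters (six in all, against two for constant variance and correlation), which is negligible with 80 women. Nothing is lost of note if the correlations prove equal: simulated power for the T1 change contrast is then about 85% under either structure.

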Participants will be randomly assigned to structured moderate-intensity aerobic exercise program or to the control group using a block randomization scheme. The study biostatistician ([name].) will generate the computer-based randomization sequence. The intervention assignment is placed in opaque envelopes and delivered to the study coordinator. After completing baseline assessments, eligible participants will be assigned to study arm by a study coordinator who will open the next one of the sequentially-numbered, sealed envelopes.

Intervention

Arm 1: Exercise Intervention Arm

Participants randomized to the exercise intervention will be required to exercise before or after each radiation treatment session, on a five-treatment per week schedule. No special accomodations will be made to open the clinic on weather days or on extra days in the event of machine failure or patient unavailability. The exercise intervention will be administered at the radiation treatment facility in a room allocated for the study. The exercise prescription consists of aerobic training utilizing the portable stationary pedal exerciser (Pedlar) which contains two cycling pedals mounted to a stationary block that allows patients to exercise while sitting. Pedal tension is adjusted to provide desired resistance. Exercise intensity is self-rated by participants, instructed that moderate intensity goal will "make you breathe somewhat harder than normal". Participants may move and position the device to permit comfortable use while sitting in a chair. Participants are required to perform 15 minutes/day of aerobic exercise using the Pedlar device on radiation treatment days; during a standard radiation course, this will typically yield 75 minutes/week of aerobic time. Ten Pedlar devices have been approved for purchase for HUMC Department of Radiation Oncology through the Development Grant. Participants will record their activity on a daily basis on an exercise log (Appendix H).

Arm 2: Control Arm

Control group participants will be told to maintain their current daily activities and exercise habits for the duration of their treatment.

Study retention and adherence

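### The mixed-model covariate screen requires a 10% association with arm, so in this randomized trial even a strongly prognostic baseline covariate is left out about nine times in ten

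*Combined protocol and SAP*

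**What the plan says.** In section e, under Statistical analysis, the mixed model is given the leading role: "The major analytical tool for addressing the specific aims of this study is linear mixed modeling for repeated measures". For each outcome, "a linear mixed repeated measures model will be fit to evaluate the main effects of time, study group, and group-by-time interaction". Covariates are then handled by a screen: "Known confounders and other covariates will be included in the linear mixed models" only "if their individual bivariate associations with both the group variable and outcome are significant at 10% level". No candidate covariates are listed for these models.

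Under Randomization, participants are allocated "using a block randomization scheme", and no stratification factor is named.

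Three other statements bear on the point:

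- The paragraph on Aims 1 and 3 hypothesizes that "participants in the intervention group will have lower average fatigue scores compared to the usual care group after the intervention".
- The same paragraph plans a separate ANCOVA of change scores, "adjusting for covariates including age". The screen does not govern that model.
- Sample size Considerations bases the 40 per arm on an ANCOVA "comparing mean fatigue score differences between the two intervention arms at the end of intervention, adjusting for baseline".

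**The concern.** Requiring an association with both exposure and outcome is a way of looking for confounders in observational data. In a randomized trial, a covariate fixed before allocation differs between arms only by chance. The test against arm therefore says nothing about whether adjustment is useful, and it rejects at its nominal rate of 10%. The reason to adjust here is precision, which depends on how strongly the covariate predicts the outcome. The rule discards strong and weak predictors alike in about nine trials out of ten.

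Two things are at stake. The first is precision for the group main effect and for any between-arm contrast at a single visit. The second is pre-specification. The candidate list is open, and which covariates enter depends on the observed balance and the outcome data, so the final model cannot be known in advance and may differ between outcomes.

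**Working it through.** **Inputs from the protocol** (Sample size Considerations): 40 per arm; means 42.53 and 37.12, difference 5.41; SDs 9.35 and 9.42, pooled SD = √((9.35² + 9.42²)/2) = 9.385, variance 88.08; baseline-to-post correlation 0.64; two-sided α 0.05.

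**Assumptions, because the documents give no figure:** compound symmetry at 0.64 over the three visits; complete data; a time-invariant covariate with correlation r to each visit, r = 0.3 to 0.5.

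**1. The plan's own figure.** The residual SD after baseline adjustment is 9.385 × √(1 − 0.64²) = 7.21. Then n = 2 × (1.960 + 1.282)² × (7.21/5.41)² ≈ 37.3, or 38 per arm. At 40 per arm, power is 91.2% (noncentral t, 77 df). The stated 40 per arm for 90% power is reproduced.

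**2. How often a covariate is kept.** The arm test passes with probability 0.10 for any r. The T1 outcome test passes in about 84 to 86% of trials at r = 0.3 and in almost all at r = 0.5. In simulation, retention was about 8% at r = 0.3 when screened on T1. It was about 9% when screened on the three-visit mean, where the correlation rises to 0.3/√((1 + 2 × 0.64)/3) = 0.34. At r = 0.5 retention was about 10% on either outcome.

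**3. Standard errors with and without the covariate.** Write v = 88.08(1 − r²) for the residual variance and c = 88.08(0.64 − r²) for the residual covariance, with r = 0 when the covariate is left out.

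| Contrast | Formula | Left out | r = 0.3 | r = 0.5 |
|---|---|---|---|---|
| Group main effect (three-visit mean) | √((2/40)(v + 2c)/3) | 1.83 | 1.72 | 1.50 |
| One visit | √((2/40)v) | 2.10 | 2.00 | 1.82 |
| Group-by-time, T0 to T1 | √((2/40)·2(v − c)) | 1.78 | 1.78 | 1.78 |

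The last row is constant because v − c = 88.08 × 0.36 whatever r is. Chance imbalance in the covariate raises the adjusted values slightly, to 1.73 and 1.51 in the first row and 2.01 and 1.83 in the second.

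**4. Power under the rule.** There were 20,000 simulated trials per scenario, with an effect of 0 at T0 and 5.41 at T1 and T2. The group main effect is then (0 + 5.41 + 5.41)/3 = 3.61.

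| Test | r | Under the rule | Always adjusted |
|---|---|---|---|
| T1 alone | 0.3 | 72.3% | 75.8% |
| T1 alone | 0.5 | 73.3% | 82.9% |
| Group main effect | 0.3 | 49.4% | 53.8% |
| Group main effect | 0.5 | 50.5% | 65.4% |

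Repeat runs agree within simulation error.

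**5. Type I error under the rule.** It was about 4.5% at r = 0.3 and 3.6 to 4.0% at r = 0.5. Simulation error is about ±0.3 points, so at r = 0.3 the departure from 5% is barely detectable. There is no sign of inflation.

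**6. When baseline fatigue is also used.** If the arm means are constrained equal at T0, the SE of the T1 effect is √((2/40)(v − c²/v)) = 1.61 without a covariate. Adding one gives about 1.60 (r = 0.3) or 1.55 (r = 0.5), allowing for chance covariate imbalance. Power by the formula goes from 91.2% to 91.8% or 93.1%.

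**The case against.** The strongest reply is that efficacy in a model with baseline among the responses is read from group-by-time, and that contrast has SE 1.78 whether or not the covariate enters. The group main effect averages in T0, where no effect can exist. A single-visit contrast ignores baseline, and no such test is explicitly listed. The 4-week comparison for Aims 1 and 3 also has change-score analyses outside the rule, with age named in advance. Once baseline is used as in the sample-size calculation, a covariate adds only about 0.6 to 2 points of power. The correlation of 0.3 to 0.5 is assumed, and nothing in the documents shows that any collected covariate is that prognostic. Estimates are not biased, and the study describes its output as preliminary evidence.

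Most of this stands as a limit on size. The group-by-time contrast is unaffected, the change-score ANCOVA is outside the rule, baseline fatigue is not dropped because it is already a response, and the loss at r = 0.3 is modest. Naming age in one model while screening it in another is a difference between models, not a contradiction.

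The point itself is not removed. The plan states that it will evaluate the group main effect in its major analytical tool, and its first hypothesis can be read as a between-arm difference after the intervention. Both lose precision under the rule. The data-dependent choice of model remains whatever r is.

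One caveat applies to the 10% figure: it holds for variables fixed before randomization. The plan does not restrict the candidates to those, and a variable measured later could be truly associated with arm.

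**Conclusion.** The concern holds. The screen keeps a prognostic baseline covariate in only about 8 to 10% of trials. Against always adjusting, it costs about 3.5 points of power (r = 0.3) to 9.6 points (r = 0.5) for a single-visit contrast, and 4.4 to 14.9 points for the group main effect. It costs nothing for the group-by-time contrast, and it does not bias the estimate or inflate type I error. These sizes rest on compound symmetry at 0.64, complete data at 40 per arm and the assumed range of r. That the arm test passes about 10% of the time rests only on randomization. The rule should be changed because it serves no purpose in a randomized comparison, leaves the model open until the data are seen, and is nearly free to replace.

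**What to change.** - Delete the 10% screening rule.
- Before outcome data are seen, name a short list of prognostic baseline covariates already collected, including age. Include them in the Aim 1 and Aim 3 mixed models and ANCOVA whatever the observed balance or p-values. The descriptive baseline table can stay, but its p-values should not choose the model.
- State how baseline enters each model. Adjust the change-score ANCOVA for the baseline value of the outcome, to match the sample-size calculation. In the mixed model, either keep baseline as a response with arm means constrained equal at T0, or move it to the covariates, but not both.

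The baseline statement is a separate gain from removing the screen, and for the T1 effect the larger one: SE 1.78 for the unconstrained T0-to-T1 contrast against 1.61 with T0 constrained. The fixed covariate then takes it to about 1.60 or 1.55.

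The cost is one sentence replaced by a named list, one sentence added on baseline, and about one degree of freedom per covariate. No new data are needed.
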